6.2.3 Rescue medication

When local pain to the index knee requires analgesic medication, the use of paracetamol/acetaminophen up to 3000 mg/day is the recommended/preferred treatment of choice during the study. In case paracetamol/acetaminophen is not effective, NSAIDs will be allowed, if the treatment follows the recommended dose and treatment duration defined by local guidelines. However, the use of indomethacin will remain prohibited due to its known inhibitory effect on GAG synthesis limiting the regenerative capacity of articular cartilage ([Dingle 1993](#), [Dingle1999](#), and [Hauser 2010](#)).

Use of rescue medication must be recorded on the Concomitant medications/Significant non-drug therapies eCRF after start of study drug.

6.2.4 Restriction for study subjects

For the duration of the study, subjects should be informed and reminded of the restrictions outlined in [Section 6.2.4.1](#).

Non-drug treatments (e.g., physiotherapy) must be reported in the Concomitant medications/ Significant non-drug therapies eCRF. Further recommendations are given in the SOM.

6.2.4.1 Dietary restrictions and smoking

- No cigarettes/use of nicotine products are allowed from Screening visit to EOS, it is not allowed to smoke 20 cigarettes or more per day **or** using of other tobacco products in amounts corresponding to 20 cigarettes or more per day.
- No alcohol for 48 hours before each dosing day.
- In order to avoid wide variations in urine volumes on PK collection days, subjects should be encouraged to have a fluid intake of approximately 240 mL every 4 hours during their waking hours, in addition to the fluid taken with meals (only on PK collection days).

6.2.4.2 Other restrictions

- After dosing, physical activity (e.g., climbing stairs, running, bicycling) should be minimized for 48-72 hours. Normal pace walking is allowed.
- No strenuous physical exercise is allowed from 48 hours prior to first dosing until study completion evaluation (e.g., weightlifting, long-distance running (>3000 m), intensive ball games (football, handball, volleyball and basketball), or tennis on a regular basis >1 time weekly). In general, activities causing heavy loading or rapid movements/rotations of the knee are not advised.
- Subjects will be required to adhere to the measures and procedures outlined by the study site, to prevent SARS-CoV-2 infections among them and clinical site staff.

6.3 Subject numbering, treatment assignment, randomization

6.3.1 Subject numbering

The subject number assigned at Screening remains the unique identifier for the subject throughout the study. For information on subject numbering, please see ‘Subject numbering’ section in the SOM.

6.3.2 Treatment assignment, randomization

This is a non-IRT study with a unique randomization list.

A treatment code will be assigned to each individual subject by way of a randomization number.

The randomization number is only used to identify the treatment to which the subject has been assigned.

If a subject requires a replacement, the replacement subject will be assigned a replacement randomization number corresponding to the original subject. Any additional subjects enrolled will use sequential subject numbering.

The randomization numbers will be generated using the following procedure to ensure that treatment assignment is unbiased and concealed from subjects and investigator staff. A randomization list will be produced by or under the responsibility of Novartis Global Clinical Supply (GCS) using a validated system that automates the random assignment of treatment arms to randomization numbers in the specified ratio.

The randomization scheme for subjects will be reviewed and approved by a member of the Randomization Office.

Follow the details outlined in the Site Operations Manual regarding the process and timing of treatment assignment and randomization of subjects.

6.4 Treatment blinding

This is a subject and investigator-blinded study. Subjects and investigators will remain blinded to study treatment throughout the study, except where indicated below.

The identity of the treatments will be concealed using unblinded site staff independent of the study team, since study treatment and placebo are not identical in appearance and odor. See details below.

Site staff

Except for any unblinded site staff identified below, all site staff (including study investigator and study nurse) will be blinded to study treatment during treatment allocation and subject dosing.

Unblinding a single subject on site for safety reasons (necessary for subject management) will occur via an emergency system in place at the site (see [Section 6.7](#)).

Site staff may also be unblinded to the treatment assignment of one or more subjects at Interim Analyses if deemed appropriate to aid decision-making.

Drug product will be supplied in bulk, so an **unblinded pharmacist** who is independent of the study team will be required in order to maintain the blind. This unblinded pharmacist will receive a randomization list or treatment allocation cards from Global Clinical Supply with the appropriate treatment allocation numbers. Appropriate measures must be taken by the unblinded pharmacist to ensure that the treatment assignments are concealed from the rest of the site staff.

Administration of study drug will be performed by an **unblinded practitioner** trained in i.a. injection procedures, who is independent of the study team. Appropriate measures must be taken by the unblinded practitioner to ensure that the treatment assignments are concealed from the rest of the site staff. Please refer to SOM for more details on administration process.

Imaging site staff

To prevent bias in the imaging analyses, all staff at the imaging site will be blinded to investigational drug throughout the study, while there is no need for blinding related to the 7T MRI measurements.

Sponsor staff or delegate

The following unblinded sponsor roles are required for this study:

The **unblinded field monitors** are required to review drug accountability and allocation at site. The unblinded monitors are not provided with a randomization list directly but will be unblinded through review of source documentation, compiled by the unblinded pharmacist, which details treatment allocation to individual subjects. The unblinded monitors will also be able to review the treatment allocation cards/randomization list provided to the unblinded pharmacist. The names of the unblinded monitor(s) are detailed in the Monitoring Plan.

The **sample analysts** will receive a copy of the randomization schedule (via request to the Randomization Office), to facilitate analysis of the samples. The sample analysts will provide the sample data to the study team under blinded conditions unless otherwise allowed.

The **study statistician** will be able to access the full randomization list from the start of the study and can share unblinded information with the rest of the clinical trial team as appropriate for internal decision purposes, as outlined in the SOM (see Blinding levels). For example, unblinded summaries and unblinded individual data can be shared with the team whenever necessary.

The study statistician is also allowed to share treatment assignments with the investigator following Interim Analyses when knowledge of the treatment assignments could aid decision-making.

The **Study programmers and other personnel involved in study data analysis** (e.g., biomarker expert) can access treatment assignment information from the start of the study for the purpose of data analysis.

The **clinical trial team** can share unblinded results with other sponsor staff (e.g., decision boards) as required for internal decision making on the study or the project while the study is ongoing. In order to monitor the scenarios described in the study and treatment arm stopping rules, the study will have a dedicated unblinded sponsor staff outside the clinical trial team.

All unblinded personnel will otherwise keep randomization lists and data or information that could unblind other study team members confidential and secure except as described above. Please refer to Blinding plan table in the SOM.

Following final database lock all roles may be considered unblinded.

Table 6-3 Blinding levels

Role	Time or Event			
	Randomization list generated	Treatment allocation & dosing	Safety event (single subject unblinded)	Interim Analysis & dose escalation
Subjects/Patients	B	B	UI	B
Site staff	B	B	UI	UI
Imaging site staff	B	B	UI	UI
Unblinded site staff (see text for details)	B	UI	UI	UI
Drug Supply and Randomization Office	UI	UI	UI	UI
Unblinded sponsor staff (see text for details)	B	UI	UI	UI
Statistician/statistical programmer/data analysts	B	UI	UI	UI
All other sponsor staff not identified above	B	UI	UI	UI

B Remains blinded

NA Not applicable

UI Allowed to be unblinded on individual patient level

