4.1 Rationale for study design

The design of this study addresses the primary objective of cartilage regeneration in subjects with mild/moderate OA of the knee and considers (i) the clinical need; (ii) clinical and preclinical data on LRX712; (iii) current practice with intra-articular injectable drugs; and (iv) the burden on patients with knee OA. The combination of frequent clinical and laboratory safety monitoring, as well as MRI with cartilage-specific pulse sequences ([Juras et al 2016](#)), performed at multiple time-points, **CCI**

██████████ will ensure appropriate evaluation of LRX712 safety, tolerability and efficacy, from both a morphological and a functional standpoint.

The parallel design ensures comparison of potential dose-dependent adverse events and distinguishes them from potential procedure (i.a. injection)-related AEs.

The study has been designed as subject- and investigator-blinded in order to ensure that both investigators and subjects remain in a state of equipoise, so that a putative difference between the treated and control groups can be interpreted as an effect of study treatment.

The study duration of 8 weeks of treatment with 11 months of monitoring after the last administration of study drug is considered adequate to monitor safety and assess potential efficacy of the drug using MRI. Randomization will be 1:1:1 (2 treatment groups:placebo), in order to also maximize statistical power for showing differences in the primary efficacy endpoint between subjects exposed to either of the two doses of LRX712 vs. placebo.

The subject population (with medial OA of the medial compartment of the knee) has been selected in order to i) ensure homogeneity in a relatively small population; ii) focus on cartilage regeneration in relatively less advanced stages of OA anchored to fmJSW 1.5-3.5 (females) or 2—4 (males); iii) maximize relevance of the findings as the medial compartment is the most frequently affected region of the knee in patients with OA ([Wise et al 2012](#)); and iv) minimize bias caused by pain from the contralateral knee affecting the reporting of pain from the index knee as well as knee function.

CCI
██████████

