10.1 Definition of adverse events and reporting requirements

10.1.1 Adverse events and adverse device effects

10.1.1.1 Adverse events

An adverse event (AE) is any untoward medical occurrence (e.g. any unfavorable and unintended sign [including abnormal laboratory findings], symptom or disease) in a subject or clinical investigation subject after providing written informed consent for participation in the study. Therefore, an AE may or may not be temporally or causally associated with the use of a medicinal (investigational) product.

The investigator has the responsibility for managing the safety of individual subjects and identifying adverse events.

Novartis qualified medical personnel will be readily available to advise on trial related medical questions or problems.

The occurrence of adverse events must be sought by non-directive questioning of the subject at each visit during the study. Adverse events also may be detected when they are volunteered by the subject during or between visits or through physical examination findings, laboratory test findings, or other assessments.

Adverse events will be assessed and graded according to the Common Terminology Criteria for Adverse Events (CTCAE).

Adverse events must be recorded under the signs, symptoms, or diagnosis associated with them, accompanied by the following information (as far as possible) (if the event is serious refer to [Section 10.1.2](#)):

1. The severity grade as per Common Terminology Criteria (CTC) AE grade.

If CTC-AE grading does not exist for an adverse event, use:

- 1=mild,
- 2=moderate,
- 3=severe
- 4=life threatening.

CTC-AE grade 5 (death) is not used, but is collected in other eCRFs (e.g., Study Completion, Death/Survival).

2. Its relationship to the investigational treatment (no/yes)
3. Its duration (start and end dates) or if the event is ongoing an outcome of not recovered/not resolved should be reported
4. Whether it constitutes a serious adverse event (SAE) See [Section 10.1.2](#) for definition of SAE
5. Action taken regarding LRX712 treatment

All adverse events must be treated appropriately. Treatment may include one or more of the following:

- Dose not changed
- Dose reduced/increased
- Drug interrupted/withdrawn

6. its outcome (i.e., recovery status or whether it was fatal)

Conditions that were already present at the time of informed consent should be recorded in medical history of the subject.

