12.7 Interim analyses

Interim analyses for exploratory and program-wide purposes may be performed at the sponsor's discretion.

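### Protocol Section 6.4 lets site staff and investigators learn the treatment of subjects still in the study at an untimed, discretionary interim analysis, which exposes the safety items that investigators judge

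*Protocol*

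**What the plan says.** Protocol Section 6.4 gives the permission in three places.

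- Under site staff: "Site staff may also be unblinded to the treatment assignment of one or more subjects at Interim Analyses if deemed appropriate to aid decision-making".
- Under sponsor staff, the study statistician is "allowed to share treatment assignments with the investigator following Interim Analyses when knowledge of the treatment assignments could aid decision-making".
- Table 6-3 has four columns: list generated; allocation and dosing; single-subject safety event; interim analysis and dose escalation. The site row reads "Site staff B B UI UI", where B means still blinded and UI means that unblinding of individual subjects is allowed. The next row reads "Imaging site staff B B UI UI".

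On interim analyses, protocol Section 12.7 says "Interim analyses for exploratory and program-wide purposes may be performed at the sponsor's discretion". SAP Section 2 plans no formal interim analysis and keeps the same discretion. Protocol Section 4.5 names decisions about this study and safety or tolerability concerns as reasons for one. Protocol Section 12.8.1 and SAP Section 7 allow the sample size to be re-assessed at one.

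On the purpose of the blind, protocol Section 4.1 says that investigators and subjects are blinded to keep them in equipoise, "so that a putative difference between the treated and control groups can be interpreted as an effect of study treatment".

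**The concern.** The design rests interpretation on the investigator's blind, and Section 6.4 then allows that blind to be lifted for named subjects on one loose test: that the knowledge would help a decision. Nothing confines the disclosure to subjects who have finished, or to staff who do not assess outcomes. An investigator who knows a subject's arm may go on grading that subject's adverse events, calling them related or not, and deciding whether treatment continues.

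Local tolerability matters a great deal here. The trial was restarted after a tolerability hold, and protocol Section 1.4 makes structural benefit relative to tolerability the basis for further development. Severity and relatedness are the parts of the tolerability record most open to an assessor's belief about treatment.

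**Working it through.** The plan gives no figure on this point, so the check is a side-by-side reading plus one labelled illustration.

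**1. Is the permission limited?** Section 6.4 has a general rule (blind throughout, with stated exceptions) and a statement that site staff are blinded while treatment is allocated and given. The interim permission is an added exception. It is not tied to the end of dosing or follow-up, and Table 6-3 repeats it without a condition.

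**2. Can an interim fall while subjects are ongoing?** Yes. No number, timing or trigger is fixed. Re-assessing the sample size implies that enrolment may follow. Each subject has 8 weeks of treatment and 44 weeks of follow-up, so any interim before the last subject's Week 52 visit finds subjects still in the study.

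**3. Which items pass through the investigator?**

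| Item | Source | Exposed? |
|---|---|---|
| Primary MRI volume | Protocol 8.3.1.1, 8.3.3: blinded independent central review, one central reader | Not directly |
| Giving the injection | Protocol 6.4: unblinded practitioner outside the study team | No |
| AE severity and relatedness | Protocol 10.1.1.1; summarized by arm under protocol 12.5.2 and SAP 5.1 | Yes |
| Arm-pausing rule | Protocol 9.1.6: depends on severity and relatedness in two subjects of one arm | Yes, through its inputs |
| Stopping a subject's treatment | Protocol 9.1.1: partly investigator judgement | Yes |
| Replacement | Protocol 9.1.2: some cases by sponsor and investigator agreement | Yes |
| AEs of special interest, Weeks 28 to 52 | Protocol 10.1.1.1 | Listings only |

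The last row follows from SAP Section 3.2. Safety summaries stop 28 days after the last dose. The last planned dose is on Day 57, so the window closes on Day 57 + 28 = Day 85, and Week 28 is Day 197.

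**4. Replacement.** Protocol Section 6.3.2 gives a replacement a randomization number that corresponds to the original subject's. Reading that as the same treatment, anyone who knows the original's arm and the link between the two knows the replacement's arm, possibly before the first dose.

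**5. Consequence of unblinding.** Section 9.1.1 makes emergency unblinding a reason to stop study treatment. No consequence is stated for interim unblinding.

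**6. Imaging staff.** The text of Section 6.4 keeps them blinded for the whole study; Table 6-3 allows unblinding at an interim. The two conflict.

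**7. Illustration: how much can one judgement matter to the pausing rule?** Take 45/3 = 15 subjects in an arm and an assumed true rate q of qualifying events, independent between subjects. The documents do not give q.

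P(exactly 1) = 15·q·(1−q)^14; P(2 or more) = 1 − (1−q)^15 − 15·q·(1−q)^14.

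| q (assumed) | Exactly 1 | 2 or more (pause) |
|---|---|---|
| 5% | 37% | 17% |
| 10% | 34% | 45% |
| 15% | 23% | 68% |
| 20% | 13% | 83% |
| 30% | 3% | 96% |

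With exactly one qualifying event, one further event judged to qualify would pause the arm. At assumed rates of 5% to 15% the arm sits there with probability 23% to 37%. This shows the leverage of a single judgement. It does not estimate how often unblinding would change one.

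**The case against.** The strongest case for the plan is that this is a deliberate choice in an exploratory study. Text and table agree on site staff, under an explicit exception clause. The permission is conditional, and the SAP plans no formal interim. An interim called for a tolerability concern could give a real reason to tell an investigator who received what. The emergency code break is not an equal substitute, since it is reserved for emergencies and leads to stopping treatment. Section 9.1.6 itself has the investigator and sponsor agree on whether subjects of a stopped arm continue, which may reveal their arm. Section 6.4 also refers to a blinding plan in the Site Operations Manual, which may contain limits not visible here. Finally, subjects who stop treatment after an emergency code break are still asked back for assessments, so an unblinded investigator can go on assessing them too.

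Much of this stands. It makes the point an exposure rather than a certain breach, and it means that any fix must deal with Section 9.1.6. It does not justify a permission with no stated limit. Section 6.5 says that no dose escalation is planned, so that part of the table column has nothing to serve, and Section 6.4 already provides dedicated unblinded sponsor staff outside the trial team to watch the stopping rules.

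A reader might go further and infer that the blind will be broken and the primary comparison compromised. The documents do not support that: no interim is certain, the primary images are read centrally by blinded reviewers, and subjects themselves stay blinded at an interim in Table 6-3.

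**Conclusion.** The point holds as an open-ended permission that exposes investigator-judged items: AE severity and relatedness, treatment discontinuation and replacement, with a further leak through replacement numbers. It is worth a cheap wording change. Sample size, alpha and power are untouched. The verdict assumes that the Site Operations Manual does not already restrict the disclosure.

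The size of any bias cannot be derived from the documents. Two stronger readings should be set aside.

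- A reader might take the first-in-human contrast in investigator-suspected related AEs as the bias at stake: 25 of 28 on LRX712 (89%) against 4 of 14 on placebo (29%), from 7 groups of 4 + 2. It compares treatments, not blinded with unblinded assessors, and it includes 40 mg and 75 mg groups that are not randomized arms under amendment 4.
- A reader might infer that later assignments become predictable. The documents do not mention blocks. Even with blocks, one disclosure helps only for the places left in the block in progress, and only if its earlier assignments are all known. The permission covers one or more subjects, not necessarily all.

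**What to change.** - **Protocol 6.4:** restrict both permissions to subjects who have had their last study visit and who have no replacement still in the study or pending. The second condition is needed because an early discontinuer may be finished while the replacement is not.
- **Table 6-3:** set site staff to B at interim analysis for all other subjects. Set imaging site staff to B at interim analysis, to agree with the text of 6.4.
- **Interim communication:** give investigators only the decision taken. Keep the emergency code break and the dedicated unblinded sponsor staff as they are.
- **Protocol 9.1.6:** reconcile it with the new wording, stating how the blind is handled when an arm is stopped and its subjects' assignments may become known.
- **SAP 5.1:** if an investigator is unblinded to an ongoing subject, flag that subject's later AEs and repeat the on-treatment severity and relatedness tables without them.

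The cost is a wording amendment, two table entries, the reconciliation with 9.1.6 and a conditional repeat of two tables. The sponsor gives up an optional disclosure for ongoing subjects.

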6.5 Dose escalation and dose modification

There is no planned dose escalation in this trial.

Investigational treatment dose adjustments and/or interruptions are permitted only under the circumstances described in [Section 9.1.1](#), [Section 9.1.5](#) and [Section 9.1.6](#).

6.6 Additional treatment guidance

LRX712 will be administered into the knee via i.a. injection which will occur at the study site. Ultrasound-guided injection for the repeated drug administration is optional. See the SOM for further details.

Sponsor qualified medical personnel will be readily available to advise on study-related medical questions or problems.

